5.5.2. Additional considerations

A summary of subjects with all combined solicited (regardless of their duration) and unsolicited AEs will be provided. Solicited AEs will be coded by MedDRA as per the following codes:

Solicited symptom	Lower level term code	Corresponding Lower level term decode
FATIGUE	10016256	Fatigue
FEVER	10016558	Fever
GASTROINTESTINAL	10017944	Gastrointestinal disorder
HEADACHE	10019211	Headache
PAIN	10022086	Injection site pain
REDNESS	10022098	Redness at injection site
SWELLING	10053425	Swelling at injection site

6. ANALYSIS INTERPRETATION

All analyses performed during this study will be descriptive. The inferential analyses will not be considered confirmatory but rather used as an estimation of the probability that an effect is true

7. CONDUCT OF ANALYSES

7.1. Sequence of analyses

The analyses will be performed stepwise:

- An interim analysis will be performed as soon as the results of the challenge phase are available on data as clean as possible, including safety and immunogenicity results, if available. This analysis will be descriptive and performed on the Adapted PPS for analysis of efficacy and on ITTS for safety. Results will be used to make a decision on future field trials.
- When all the remaining data up to Day 190 will be available, the main analysis will be performed. An integrated clinical study report containing all data will be written and made available to the investigators.

If the data for exploratory assessments become available at a later stage, (an) additional analysis/analyses will be performed and results will be reported in a publication, if applicable.

Description	Disclosure Purpose
Interim Efficacy analysis	Internal, publication/congress presentation
Final analysis	Web disclosure, Study report

7.2. Statistical considerations for interim analyses

A descriptive analysis to evaluate vaccine efficacy against infection of *P. falciparum* will be performed on the Adapted PPS for analysis of efficacy at the time of the interim analysis and will not be part of the CSR. Note that the main objective of the study linked to this endpoint will be analysed at the end of the study, on the PPS for analysis of immunogenicity and efficacy and can output different results. At the same time, we will perform some immunogenicity and safety/reactogenicity analyses, on data as clean as possible. All the analyses will be re-done during the final analysis which will be presented in the CSR.

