### 11.4. Determination of sample size

The target enrollment for the MALARIA-092 study was ~130 vaccinated subjects (~26/vaccine group) and up to 30 subjects (or 4-6 per day, depending on the expected number of days of challenge) in the infectivity control group. Approximately 20 subjects in each group were expected to undergo sporozoite challenge (~100 vaccinated subjects overall). Based on past experience, an approximate 20% will refuse to participate in the booster study and there will be an approximate 20% drop-out rate in vaccinees for the booster study. With an assumed vaccine efficacy (VE) of ~68% in the primary study, there will be a minimum of ~20 subjects per group in this MALARIA-102 study. In addition, up to 24 infectivity control subjects will be newly enrolled for this study.

Assuming at least 19/20 controls and 6/20 vaccinees become positive (VE of ~68%), the trial has 99% power to detect statistically significant vaccine efficacy of each of the vaccination groups over the infectivity controls (p-value < 0.05).

The power to detect a statistically significant VE of each of the vaccination groups over the infectivity controls (p-value < 0.05) is presented in the table below:

Controls (N)	Vaccines (N)	Vaccine efficacy (%)	Protected controls (N)	Protected vaccinees (N)	Power* (%)
20	20	89	1	18	100
20	20	78	1	16	100
20	20	68	1	14	99.1
20	20	58	1	12	94.6
20	20	47	1	10	81.8

\*Two independent proportions power analysis - Test statistic: Fisher exact test

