### 11.13.1. Sequence of analyses

The analyses will be performed stepwise:

- An interim analysis will be performed as soon as the results of the challenge phase will be available on data as clean as possible, including safety and immunogenicity results, if available. This analysis will be descriptive and performed on the Adapted PPS for analysis of efficacy. Results will be used to make a decision on future field trials.
- When all the remaining data up to Day 190 will be available, the main analysis will be performed. An integrated clinical study report containing all data will be written and made available to the investigators.

If the data for exploratory assessments become available at a later stage, (an) additional analysis/analyses will be performed and results will be reported in a publication, if applicable.

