5.3. Efficacy

5.3.1. Analysis of efficacy planned in the protocol

The analysis of efficacy will be performed on the PPS for analysis of immunogenicity and efficacy.

Efficacy will be assessed by comparison of *P. falciparum* parasitemia incidence and time-to-onset of *P. falciparum* parasitemia after sporozoite challenge. The analysis of the primary objective will be based on blood smears results; additional exploratory analyses will be performed based on PCR results (tertiary objectives).

Vaccine efficacy (VE) is defined as $100 * (1 - \text{Relative Risk})$. Relative risk of infection and 95% CI will be calculated.

Fisher's Exact test will be used for the comparison of *P. falciparum* parasitemia incidence after challenge between each one of the study groups (P-Fx and NP-Fx) and the infectivity control group.

Kaplan-Meier analysis will be performed on time-to-onset of *P. falciparum* parasitemia, for comparisons between each one of the study groups (P-Fx and NP-Fx) and the infectivity control group, using the log-rank statistic.

The same methodology will be applied for the evaluation of the study groups (P-Fx vs. NP-Fx) versus each other. If there are sufficient evaluable subjects (at least a 1:2 ratio between vaccinated and control groups) to draw some conclusions, descriptive analyses based on initial group assignment versus control will be performed.

All statistical tests will be two-tailed at 5% significance level.

Risk periods

For the analyses of time-to-onset of parasitemia (Kaplan-Meier and log-rank), time-at-risk will start on first day of challenge. Time-at-risk will be censored on Visit 22 (Day 50; 28 days post-challenge), drop-out date, start date of anti-malarial treatment or date meeting an endpoint, whichever occurs first. Time-at-risk will be calculated as: censor date – challenge date + 1.

For the analysis of proportion affected (relative risk), all subjects included in the PPS for analysis of immunogenicity and efficacy will be considered at risk of infection and no censoring or elimination will be applied for subjects not completing the entire protocol defined post-challenge follow-up (Day 50; 28 days post challenge).

Case definition

The following will be used as case definition of *P. falciparum* infection:

Asexual blood stage *P. falciparum* parasite density > 0 detected by blood slide reading (or PCR for tertiary objectives).

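### Vaccine efficacy on the Adapted PPS informs the field-trial decision and publication but is kept out of the study report, where efficacy is planned on the PPS only

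*SAP*

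**What the plan says.** **Timing and use.** SAP 7.1 and protocol 11.13.1 place an interim analysis as soon as challenge-phase results are available, on data as clean as possible. For efficacy it is descriptive and uses the Adapted PPS. SAP 7.1 adds: "Results will be used to make a decision on future field trials". The disclosure purpose given there for the interim efficacy analysis is "Internal, publication/congress presentation"; the final analysis is for web disclosure and the study report.

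**Place in the report.** SAP 7.2 says VE is analysed "on the Adapted PPS for analysis of efficacy at the time of the interim analysis and will not be part of the CSR". The main objective "will be analysed at the end of the study, on the PPS for analysis of immunogenicity and efficacy and can output different results". The section closes by saying that all analyses will be repeated at the final analysis, which goes into the CSR. Protocol 11.13.2 has the same warning about different results but does not exclude anything from the CSR. Protocol 11.13.1 says: "An integrated clinical study report containing all data will be written". SAP section 8 lists no changes from the planned analyses.

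**Final efficacy set.** SAP 5.3.1: "The analysis of efficacy will be performed on the PPS for analysis of immunogenicity and efficacy". Neither SAP 5.3.1 nor protocol 11.9 names an Adapted PPS or ITTS sensitivity analysis.

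**How the sets differ.** In SAP 4.2.3.1, codes 800, 900, 1030, 1070 and 3000 apply to both sets. Ten codes apply to the PPS only: 1040, 1080, 1090, 2010, 2040, 2050, 2080, 2090, 2100 and 2120. Codes 2090 (blood sample schedule) and 2100 (anti-CS serology availability) are marked as applicable at all visits.

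**The concern.** Follow-up for the primary endpoint is censored at Visit 22, nominally Day 50. The interim therefore already holds every primary outcome, apart from later cleaning. The final analysis, after Day 190, answers the same primary question from the same challenge in a set that can only be equal or smaller.

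As written, the estimate that informs the field-trial decision and may reach a journal or congress is not clearly in the study report, and the estimate in the report is not the one acted on. A reader of the CSR could not tell whether the two agreed or which subjects made the difference.

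The timing sharpens this. The study is open-label, and a positive slide triggers treatment at once, so each outcome is known at the site by about Day 50. Some PPS decisions can come later. Code 2090 refers to the SAP Table 1 intervals, which include Visit 22 to Visit 23 (126 to 154 days), so a mistimed Day 190 visit could remove a subject from the efficacy analysis after the slide outcome is known.

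**Working it through.** **Inputs.** From protocol 11.4: "Assuming at least 19/20 controls and 6/20 vaccinees become positive (VE of ~68%), the trial has 99% power", with 20 per group and Fisher's exact test. Its table runs from 2/20 to 10/20 infected vaccinees (VE 89% to 47%) against 19/20 infected controls. From SAP 5.3.1: VE = 100 × (1 − relative risk), and "All statistical tests will be two-tailed at 5% significance level".

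**Assumption.** The documents do not forecast PPS-only exclusions. I take 2 to 4 of 20 vaccinees (10% to 20%) and leave controls at 19/20.

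**1. Reproduce the plan.** VE at 6/20 is 100 × (1 − 0.30/0.95) = 68.4%. Exact two-sided Fisher power at 0.05 is 99.7%, against 99.1% stated, so the headline stands. The lower rows give 97.4% (stated 94.6%) and 89.4% (stated 81.8%). The stated 99.1, 94.6 and 81.8 match a two-sided 0.025 level, so the table is conservative for the 5% level in the text.

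**2. Extremes at the planned 6/20.**

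| Dropped | All infected | VE | All uninfected | VE |
|---|---|---|---|---|
| 2 | 4/18 | 1 − 0.2222/0.95 = 76.6% | 6/18 | 1 − 0.3333/0.95 = 64.9% |
| 4 | 2/16 | 1 − 0.125/0.95 = 86.8% | 6/16 | 1 − 0.375/0.95 = 60.5% |

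The largest p-value among these is 0.0003. The estimate moves; the conclusion against controls does not.

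**3. Lowest planned row, 10/20.** VE is 47.4%, p = 0.003. Dropping four uninfected gives 10/16, VE 34.2%, p = 0.030. Significance holds even here.

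**4. Where significance does change.**

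| Infected controls | Adapted PPS | p | PPS | p |
|---|---|---|---|---|
| 19/20 | 14/20 (VE 26.3%) | 0.092 | 13/19, one infected dropped (VE 28.0%) | 0.044 |
| 19/20 | 13/20 (VE 31.6%) | 0.044 | 13/18, two uninfected dropped (VE 24.0%) | 0.083 |
| 19/20 | 12/20 (VE 36.8%) | 0.020 | 12/16, four uninfected dropped (VE 21.1%) | 0.149 |
| 18/18 | 15/20 (VE 25.0%) | 0.048 | 15/19, one uninfected dropped (VE 21.1%) | 0.105 |

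**5. Exclusions unrelated to outcome.** Simulation with 20 vaccinees, control infection probability 0.95, vaccinees dropped at random with probability 10% or 20%, and 40,000 runs per scenario. Share of trials in which the two sets fall on opposite sides of p = 0.05:

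| True VE | 20 controls | 6 controls |
|---|---|---|
| 68% | 0.2% to 0.6% | 4.3% to 6.6% |
| 58% | 1.2% to 2.4% | 7.0% to 10.7% |
| 47% | 3.5% to 6.5% | 7.3% to 10.9% |
| 26% | 8.4% to 11.6% | 1.0% to 1.9% |

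The mean absolute shift in VE is about 3 to 5 points and the 95th percentile about 8 to 12 points. Six is the lower end of the control range in protocol Table 1.

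**The case against.** **What stands.** Both documents name the PPS analysis at study end as the one for the main objective and warn that the interim may differ. A reader might infer that there is no rule for which result counts; there is. The two sets also have a plain reason: the PPS requires immunogenicity data, which the interim may not yet have.

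A reader might also infer double testing and inflated type I error. The documents do not support that. The interim is called descriptive, no test is named for it, and SAP section 6 treats all inferential results as non-confirmatory.

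Nor can it be said that the final analysis only removes subjects. Interim data are not fully cleaned, and protocol 6.4.1.4 archives slides for possible re-examination, so outcomes might be corrected too.

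Two readings of the text need care. Code 2050 covers only conditions forbidden by the protocol, so it is not open-ended judgement. Code 2100 may mean no anti-CS result at any visit rather than one missing visit; the PPS definition, which asks for a result on at least one antigen after Day 1, favours the lenient reading. Code 2090 is the clearer route to late exclusion.

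**What does not dispose of the point.** The closing sentence of SAP 7.2 can be read as saying that only the uncleaned run stays out of the CSR and a clean repeat goes in. That is plausible, but SAP 5.3.1 plans efficacy on the PPS alone, so whether VE on the Adapted PPS is repeated remains unclear. The protocol's promise of a report with all data is likewise not a flat contradiction, since it need not mean every interim output. Descriptive status does not settle the matter either: it makes the point estimate the main product, and that is what moves. The planned counts of PPS exclusions do not show the slide outcomes of those excluded.

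**Conclusion.** The point holds as a gap in reporting and traceability. Precedence is set, but nothing clearly requires the CSR to show the VE estimate that informed the field-trial decision, or to identify the subjects who separate it from the main result.

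The size is modest at planned efficacy. With about 20 controls and VE of 47% to 89%, none of the cases checked with up to four exclusions lost significance. At 6/20 infected, the estimate could move from 68.4% to between 64.9% and 76.6% (two dropped) or between 60.5% and 86.8% (four dropped). Changes in significance arise mainly at VE of about 20% to 30%, reaching about 37% when four uninfected subjects go, or when controls are few. NP-Fx would be the group exposed if its efficacy proved low.

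These ranges rest on assumed exclusions of 10% to 20% of vaccinees, none among controls, and extreme allocations by outcome in the tables of fixed counts. A reader might conclude that one to three exclusions could overturn the trial's planned result; the figures do not show that.

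**What to change.** 1. **SAP 7.2:** delete the closing clause of the first sentence that keeps the interim VE analysis out of the CSR.
2. **SAP 5.3.1:** keep the PPS as the main analysis. Require VE with 95% CI, Fisher's exact test and log-rank for P-Fx and NP-Fx versus controls on the Adapted PPS, from the final clean data, as a sensitivity analysis beside the PPS results in the CSR. Add a note giving the interim estimate used for the field-trial decision.
3. **Listing:** show each subject in the Adapted PPS but not in the PPS, with elimination code and slide outcome.

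The cost is SAP wording, one extra pair of tables and one listing. Sample size, power and conduct do not change. The one downside for the sponsor is that any discordance becomes visible.

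Assigning the codes that depend only on data to Day 50 before slide results are tabulated by group is optional and only partly effective: slides are read in real time in an open-label study, and codes that depend on Day 190 cannot be settled then.

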8. CHANGES FROM PLANNED ANALYSES

Not applicable.

9. ANNEXES

9.1. Business rules for standard data derivations and statistical methods

This section contains GSK Vaccines' standard rules for data display and derivation for clinical and epidemiological studies.

9.1.1. Attributing events to vaccine doses

The dose relative to an event is the most recent study dose given to a subject prior to the start of a given event.

If an event starts on the same day as a study dose, the relative dose will be derived from the additional information provided in the CRF using the contents of the flag indicating if the event occurred before or after vaccination. If 'after vaccination' is selected, the relative dose for the event will be the one administered on the start day of the event. If 'before vaccination' is selected, the relative dose for the event will be the dose prior to this one.

9.1.2. Handling of missing data

9.1.2.1. Dates

When partially completed dates (i.e. with missing day or month) are used in calculations, the following standard rules will be applied:

- A missing day will be replaced by 15
- A missing day and month will be replaced by June 30th.

The following exceptions apply:

- AE start dates with missing day:
 - If the event starts in the same month as the study dose, the contents of AE.AESTRTPT (the flag indicating if the event occurred before or after vaccination) will be used to complete the date. If 'after vaccination' is selected, the imputed start date will match the study dose given during that month. If 'before vaccination' is selected, the imputed date will be one day before the study dose given during that month.
- AE start dates with missing day and month:
 - If the event starts in the same year as the study dose, the contents of AE.AESTRTPT (the flag indicating if the event occurred before or after vaccination) will be used to complete the date. If 'after vaccination' is selected, the imputed start date will match the study dose given during that year. If 'before vaccination' is selected, the imputed date will be one day before the study dose given during that year.

All other cases of incomplete AE or concomitant medication/vaccination start date will follow the standard rules above.

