### Overview of the recruitment plan

On or about the last study visit of the MALARIA-092 study, participants will be asked about their willingness to be contacted to take part in a booster study, which will also be conducted at WRAIR. The investigator and his team will explain the rationale for MALARIA-102 and explain in general terms what the study entails. Only subjects who have completed all vaccinations and the primary challenge will be eligible for screening for the MALARIA-102 study. Such subjects who are interested in continuing on to participation in the MALARIA-102 study will be contacted and scheduled for a screening visit during the approved study recruitment window. Screened subjects who fulfill all inclusion criteria (and none of the exclusion criteria) for the study will be considered eligible to participate in the study.

For the infectivity control group, subjects will be recruited and screened in order to provide approximately 6 control subjects for each malaria challenge day required for the trial (the number of which will depend on the final number of experimental subjects). Up to 24 subjects may eventually be enrolled (defined as undergoing malaria challenge) as infectivity controls.

To be deemed eligible to participate, control subjects must fulfill all inclusion criteria (and none of the exclusion criteria) for the study. For the infectivity control group **only**, in the rare event that malaria-naïve volunteers cannot be recruited, subjects may be enrolled if they have not been diagnosed with malaria (clinical disease or parasitemia) within the last five years (inclusive).

WRAIR has an established process whereby an IRB-approved generic screening protocol is used to screen potential subjects managed by the WRAIR Clinical Trials Center. If subjects from this pre-screened group agree to be infectivity controls in the MALARIA-102 study, the required biochemistry, hematology, HIV, HCV and HBsAg and ECG test results can be rolled over to the study provided they occur within the screening period, at the discretion of the Principal Investigator.

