5.5. Analysis of safety and reactogenicity

5.5.1. Analysis of safety and reactogenicity planned in the protocol

The analysis of safety will be performed on the ITTS.

For the P-Fx and NP-Fx groups:

- The percentage of subjects with at least one local AE (solicited and unsolicited), with at least one general AE (solicited and unsolicited) and with any AE during the 7-day or 21-day follow-up period after the booster Fx dose will be tabulated with exact 95% CI. Same computations will be done for grade 3 AEs, for any AEs considered related to vaccination and for any grade 3 AEs considered related to vaccination.
- The percentage of subjects reporting each individual solicited local AE (any grade and grade 3) and each individual solicited general AE (any grade, grade 3, any related, grade 3 related, resulting in medically attended visit) during the 7-day follow-up period (Days 1-7) after the booster Fx dose will be tabulated for each group, with exact 95% CI.
- For fever (defined as temperature $\geq 37.5^{\circ}\text{C}/99.5^{\circ}\text{F}$ for oral, axillary or tympanic route), the number and percentage of subjects reporting fever by half degree ($^{\circ}\text{C}$) cumulative increments during the first seven days (Days 1-7) after the booster Fx dose will be tabulated. Similar tabulations will be performed for any fever with a causal relationship to vaccination and grade 3 ($> 39.0^{\circ}\text{C}$) causally related fever. The maximum temperature reported over the 7-day follow-up period will be tabulated.
- The percentage of subjects reporting unsolicited AEs within 21 days (Days 1-21) after the booster Fx dose will be tabulated by group and by MedDRA preferred term with exact 95% CI. Similar tabulation will be done for grade 3 unsolicited AEs, for any causally related unsolicited AEs and for grade 3 causally related unsolicited AEs.
- The percentage of subjects using concomitant medication (any medication, any antipyretic and any prophylactic medication, respectively) during the 7-day follow-up period after vaccination will be summarized by group.

For all subjects:

- The percentage of subjects reporting AEs during 29 days after the sporozoite challenge (Day 22-Day 50) will be tabulated by group and by MedDRA preferred term with exact 95% CI. Similar tabulation will be done for grade 3 unsolicited AEs, for any causally related unsolicited AEs and for grade 3 causally related unsolicited AEs post challenge.

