9.1.3.4. Onset day

The onset day for an event (e.g. AE, medication, vaccination) is the number of days between the study vaccination and the start date of the event. This is 1 for an event occurring on the same day as a vaccination (and reported as starting after vaccination).

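### The partial-date rule in SAP 9.1.2.1 never uses the challenge date, so an AE with a missing start day can land in the wrong safety table if tables are assigned by imputed date (minor)

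*SAP*

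**What the plan says.** SAP 9.1.2.1 (Dates) sets the default for partial dates: "A missing day will be replaced by 15". AE start dates with a missing day have one exception. If the AE falls in the calendar month of the dose, a before/after-vaccination flag is used, and for an AE after vaccination "the imputed start date will match the study dose given during that month". The rest go back to the default: "All other cases of incomplete AE or concomitant medication/vaccination start date will follow the standard rules above".

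The neighbouring rules also look only to the vaccine. SAP 9.1.1 reads "The dose relative to an event is the most recent study dose given to a subject prior to the start of a given event", and the onset day in SAP 9.1.3.4 "is the number of days between the study vaccination and the start date of the event".

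SAP 5.5.1 divides the AE tables at the challenge:
- For the two vaccinated groups: "The percentage of subjects reporting unsolicited AEs within 21 days (Days 1-21) after the booster Fx dose will be tabulated by group".
- Across all three study groups, the second table reads: "The percentage of subjects reporting AEs during 29 days after the sporozoite challenge (Day 22-Day 50) will be tabulated by group". This table includes the infectivity controls, who receive no dose.

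SAP Table 1 allows 21 to 28 days between dose and challenge.

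**The concern.** The two tables separate what followed the booster from what followed the infection. The date rules come from the sponsor's standard annex and have no anchor at the point where these tables divide.

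Three errors are possible when the start day is missing:
- A post-challenge AE can be dated before the challenge. In a vaccinee it may then be counted in Days 1-21, where a likely effect of infection looks like booster reactogenicity.
- A post-challenge AE can be dated past the 29-day window and drop out of the challenge table.
- A Days 1-21 AE in the month after the dose can be dated on or after the challenge and be counted as post-challenge.

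The dose-month exception cannot apply to a control, so only the 15th remains. That date may come before AE recording starts for that subject.

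**Working it through.** The plan gives no figure on this point, so there is none to reproduce. I applied the SAP rule as written.

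**Inputs.** Default to the 15th and dose-month exception (SAP 9.1.2.1); windows of 21 and 29 days (SAP 5.5.1); dose-to-challenge gap of 21 to 28 days (SAP Table 1).

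**Assumptions.** Month known, day missing, vaccination flag correct, table assigned by imputed date. Onset is spread evenly over each window and dates over a 365-day year (2019 calendar).

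**Single cases, 21-day gap**

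| Dose | Challenge | True onset | Imputed to | Effect |
|---|---|---|---|---|
| 4 March | 25 March | 29 March (Day 26) | 4 March (Day 1) | moves to Days 1-21, by the dose-date rule |
| 28 January | 18 February | 21 February (Day 25) | 15 February (Day 19) | moves to Days 1-21, by the 15th |
| 20 March | 10 April | 4 April (Day 16) | 15 April (Day 27) | moves to the challenge table, by the 15th |

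**One challenge date by hand.** Challenge on 25 March; the window is 25 March to 22 April.
- In a control, onsets on 25-31 March (7 days) become 15 March, before the challenge. Onsets on 1-22 April (22 days) become 15 April, inside.
- Share outside = 7/29 = 24.1%.
- In a vaccinee dosed on 4 March, the same 7 days become 4 March, so the share outside is again 7/29.

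**Extremes.**
- Challenge on 16 March (window to 13 April): 16 March days become 15 March, one day early, and 13 April days become 15 April, two days late. Outside = (16 + 13)/29 = 100%.
- Challenge on 1 January: all 29 days become 15 January. Outside = 0/29.

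**Post-challenge AEs, all 365 challenge dates x 29 onset days = 10,585 cases.** Outside the window: 1,523 before challenge (14.4%) + 1,260 after the window (11.9%) = 2,783, or 26.3%. Per challenge date the median is 7/29, the middle half of dates runs from 3/29 to 11/29, and the range is 0/29 to 29/29.

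Vaccinee and control counts agree at every date. The reason is simple: if the dose and a post-challenge AE share a calendar month, the challenge is on the 22nd or later, so the 15th would also precede it.

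| Gap (days) | Moved out by dose-date rule | Moved out by the 15th | Post-challenge AEs counted in Days 1-21 | Days 1-21 AEs dated on or after challenge |
|---|---|---|---|---|
| 21 | 5.6% | 20.7% | 14.4% | 16.4% |
| 24 | 2.7% | 23.6% | 9.5% | 10.3% |
| 28 | 0.5% | 25.8% | 4.5% | 4.4% |

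Columns 2 to 4 apply to vaccinees; in controls the 15th accounts for all 26.3%. The last column comes from 365 dose dates x 21 onset days, and the dose-date rule contributes nothing to it.

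**The trial has few challenge dates, so the yearly average may not apply.** The protocol plans "approximately 6 control subjects for each malaria challenge day required for the trial" and at most 24 controls, so 24/6 = about 4 challenge days at that rate. If they are consecutive (an assumption), a 4-day block gives 0.9% to 73.3%, median 22.4%.

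**Malaria-timed onset.** Protocol 6.4.1.5 gives a pre-patent range in controls of 7-18 days. For onsets on those days the mean share outside is 13.7%. The median is 0%, and no such day is misdated on 64.1% of challenge dates.

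**The case against.** The strongest reply is that the imputed date may never decide the table. Protocol Table 4 lists post-vaccination and post-challenge AEs as separate items documented in the eCRF, and Protocol 9.3.1 sends AEs to the appropriate eCRF section. The eCRF and the table shells (SAP 9.2 places these in the trial master file) are not in the documents. This stands as a condition on the point. It does not remove it, because the SAP never says that record type overrides the date.

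Second, missing start days should be rare. Subjects are seen daily on Days 27-40 and then about every two days. Diary cards are checked at Visits 2 and 3, and omissions are queried and source-verified (Protocol 12.1 and 12.2). A control AE dated before challenge would look wrong on review. All of this stands, and the documents give no count from which to derive an expected number of misplaced AEs.

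Third, the shares count onset days, while the tables report percentages of subjects, by preferred term. A moved AE changes a cell only if it was that subject's only qualifying event there. This also stands.

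A reader might infer more: that about a quarter of post-challenge AEs will be misplaced, that the rule tilts the vaccinee-control comparison, or that efficacy is affected. The documents support none of these. The 26.3% applies only to AEs with a missing day, and the share outside the window is the same in both groups at each challenge date. The efficacy endpoint is a slide result, not an AE start date.

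**Conclusion.** The point holds in conditional form and is minor. The stated rule does not fit a design whose AE tables divide at the challenge. It misplaces AEs when two conditions meet: a missing start day, and assignment by imputed date. Given both, the share of post-challenge onset days dated outside the window is 26.3% averaged over a year, and anything from 0 to 100% for a particular challenge date. The 15th does most of this; the dose-date rule contributes 5.6% or less. The averages rest on uniform dates and uniform onset.

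The effect on any tabulated percentage cannot be derived from the documents and should be small. All analyses are declared descriptive (SAP 6). The vaccinee SAE and specific-interest tables run from Day 1 to Day 190, so a move between the two windows does not change them. The corresponding control tables run only from challenge to Day 50, so the same default could in principle matter there.

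**What to change.** Add to SAP 9.1.2.1 and 5.5.1:

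1. The AE record type (post-vaccination or post-challenge) assigns the table. No imputed date moves an AE across the challenge.
2. For AEs recorded as post-challenge, in all groups including controls, a missing day is imputed as the later of the challenge date and the first of the reported month, and no later than the end date if known.
3. For AEs recorded as before challenge, keep the dose-date rule. Otherwise use the first of the reported month instead of the 15th.
4. When the dose-to-challenge gap exceeds 21 days, an AE known to start on Day 22 or later but before challenge is not counted in Days 1-21.

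Rule 2 cannot fail if the record type is correct: the imputed date is never before the challenge and never later than the true onset. Over 3 years of dose dates and gaps of 21-28 days, 0 of 254,040 post-challenge cases and 0 of 183,960 Days 1-21 cases left their window under rules 2 and 3.

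Rule 4 is needed because rule 3 alone would date AEs from those in-between days into Days 1-21 in 93% of cases at a 24-day gap and 87% at 28 days. Such records should be rare, since the general AE recording periods in Protocol 9.3.1 do not cover those days.

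The cost is a few lines of SAP text and code, plus a before/after-challenge flag if the eCRF does not already separate these AEs. Visit number should not stand in for that flag, because Visit 3 is both the challenge visit and the visit at which the Days 1-21 diary is returned.
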